### **Study Intervention.**

*Intervention Arm:* Men who are randomized to the intervention arm will be invited to a peer health education session, either in-person or virtually. Eighty-eight of the 176 men will be randomized to this group, and we will host sessions that attract roughly 6-8 men at a session. Our previous experience conducting peer health education sessions found that 6-8 men was an ideal attendance level, as it allowed for interaction and discussion but did not feel overwhelming. Each session will be facilitated by two peer educators, who can share responsibilities and interact with each other. We expect to offer 12-15 sessions, or roughly 1-2 sessions per month. Sessions will be scheduled at various times of the day and days of the week, to accommodate men with varying schedules and commitments. Each peer educator will be compensated for 2 hours of time to run a session from start to finish, being compensated at \$20/hour.

First, the peer educator will introduce the topic of PCA, so that men understand the disease and how it relates to their health. The educator will lead a discussion regarding PCA risk, family history, PCA genetics, considerations of genetic testing, implications of genetic testing on family and self, and financial and ethical considerations. The discussion is meant to be interactive, with men sharing stories and experiences and peer educators answering questions and clarifying facts. All information will be delivered in a culturally appropriate manner by peer educators who are from the community they are serving. Immediately following the discussion, men will complete a post-survey to measure short-term changes knowledge about prostate cancer and genetic testing, thoughts about cancer, in decisional conflict about genetic testing, attitudes toward genetic testing, subjective norms about testing, and intentions to seek genetic testing. We will also get feedback on the peer-led session.

*Control Arm:* After providing informed consent and completing the baseline survey over the telephone or in-person, eighty-eight men will be randomized to this arm and each man will receive an educational booklet. It is expected that materials will be mailed within 24 hours of the

---

telephone call or provided to the participant in person. The information will cover PCA risk, family history, PCA genetics, considerations of genetic testing, implications of genetic testing on family, and financial and insurance considerations.

**Endpoint Survey.** All men, regardless of study arm, will complete an endpoint survey. A member of the study team will call each participant two months after either attending a peer education session (intervention arm) or being mailed the educational print materials (control arm). Previous research shows that two months is an adequate amount of time to digest the material and act upon it, if desired. The majority of items on the baseline survey, except for the demographic information, will be repeated on the endpoint survey. Participants who are not reached by telephone will be contacted by mail and by email to attempt to retain the maximum number of participants over time.

**Participant Compensation.** Each man who participates in all study-related activities will receive \$50 over the course of the study. Men in the intervention group will receive \$25 for completing the baseline survey via the mail and \$25 for completing the endpoint survey over the telephone at two-months post-intervention. Men in the control group will receive \$25 in their mailed packet of materials after completion the baseline survey and an additional \$25 for completing the endpoint survey over the telephone at two-months post-intervention.

**Referral to Genetic Counseling.** Men from both groups who decide they want to proceed with genetic counseling and genetic testing will be given the number to contact the Cancer Risk and Genetics Program at Sidney Kimmel Cancer Center at Jefferson, led by [name] (study PI). Once men contact the Genetics Program, an intake will be performed to determine if they meet personal or family history criteria for genetic testing. Current NCCN criteria for PCA genetic testing include any of the following: (1) personal history of advanced or metastatic PCA, (2) family history of brother, father, or multiple family members diagnosed with PCA at age <60, (3) first-degree, second-degree, or third-degree relatives with cancers of the breast, ovary, prostate, pancreas, colon, or endometrium suggestive of a hereditary cancer syndrome. Men will then be scheduled for a genetic counseling visit to formally cover information regarding genetic testing such as how cancers can be inherited, types of genetic test results, and implications for the man and his family. Once the man agrees to proceed with testing, a saliva sample will be collected and sent to Invitae, a CLIA-certified and experienced clinical genetic testing laboratory to perform multigene testing. Genes to be tested by sequencing and deletion/duplication testing will include *BRCA1*, *BRCA2*, *ATM*, *PALB2*, *CHEK2*, *NBN*, the DNA mismatch repair genes, and additional genes as needed. Invitae follows ACMGG guidelines for variant classification and all standard procedures for variant reclassification updates. Since men in this study may be underinsured, the study will pay for the cost of genetic testing for all men who undergo genetic counseling. Once

---

results return, men will be called to come in for a results disclosure visit to discuss their results and answer any questions.

**Assessment of genetic counseling experience.** Since genetic testing of AA men is a novel field and is understudied, we will take the opportunity to survey men about their genetic counseling experience at the pre-test counseling visit and the post-test visit. We will use the Satisfaction with Genetic Counseling Scale, a 6-item validated measure with responses entered on a Likert scale ranging from “Strongly Agree” to “Strongly Disagree”. The questions include: (1) The provider or staff member seemed to understand the stresses I was facing; (2) The provider or staff member helped me to identify what I needed to know to make decisions about genetic testing; (3) I feel better about my health after meeting with this provider or staff member; (4) The session was about the right length of time I needed; (5) The provider or staff member was truly concerned about my well-being; and (6) The session was valuable to me.

At the post-test visit, we will also administer a survey developed regarding knowledge and understanding of genetic test results, which has previously been published by the study team in a male population undergoing genetic testing. This survey includes questions about the man’s genetic test results (“I was found to carry a genetic mutation” or “I was found to carry a variant of uncertain significance”), interpretation of the results (“I am at higher risk for PCA based on my genetic result” or “My children are recommended to be tested based upon my genetic result”), and sharing of genetic results with family and providers.

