**Participant Recruitment and Study Enrollment.** MEE Productions, Inc. will develop culturally-tailored recruitment materials including flyers, posters and email blasts for CityLife Clinics to send to their AA male patients. The goal is to enroll 176 men in the study. We are anticipating a roughly 15% attrition rate over the course of the intervention, producing a final sample size for analysis of 150 men. We anticipate, based on our previous experience in community-based research, that we will have to screen about 10 times that number, or about 2000 men, to reach our study recruitment goal of 176 men. The research team will work with CityLife Clinic to mail a study recruitment letter to eligible males at their clinic, inviting them to participate. A toll-free, local telephone number will be included in the letter for men to opt-out of the study. After two weeks, any male who has not opted out will receive a telephone call from a member of the research team to screen for study eligibility. We will supplement our recruitment at CityLife Clinic by grassroots outreach in the neighborhood surrounding the clinic, to invite men not associated with the clinic to participate. We will promote the study at community recreation centers, public libraries, housing complexes and apartments, local non-profit organizations, barbershops, and employment agencies. Men who see the flyers or a member of the study team in the community can also call the toll-free, local number to screen for eligibility and participate. This is a similar approach that the study team was successful in using for the previously funded DOD study.

**Study eligibility.** Men who call the telephone number associated with the study or are who approached in the community will be screened for eligibility by the study research manager. Any AA male with or without prostate cancer between the ages of 35-69 will be eligible for the study. Men must speak and read English comfortably, as all study materials will be in English. Men do not need to be established patients at CityLife Clinics to participate.

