**Study Randomization and Informed Consent.** Those who are eligible to participate will be randomized to either the intervention or the control arm. Men randomized to the intervention arm will be scheduled to attend a health education session hosted at CityLife Clinic or virtually, while men who are randomized to the control arm will receive educational materials about PCA genetic testing in the mail or in person. All men who agree to participate will be read a consent statement over the phone or in person and will verbally agree to consent to participate. A copy of the consent statement will be provided to them for their records.

**Baseline Survey.** All participants will complete a brief baseline questionnaire over the telephone or in person with the study manager. Items to be assessed at baseline include knowledge about prostate cancer, their personal family cancer history, knowledge of genetic testing and screening, attitudes towards genetic testing, subjective norms about genetic testing, decisional conflict about genetic testing, and intentions to seek genetic counseling. Knowledge about PCA genetics and genetic testing will be measured using a 14-item scale, recently published by the study team in a population of men undergoing genetic testing. The measure for decisional conflict will be the SURE Decisional Conflict Scale, a low-literacy validated measure to screen for decisional conflict. The four questions encompass the following with Yes/No responses: (1) Do you feel sure about the best choice for you? (2) Do you know the benefits and risks of your options? (3) Are you clear about which benefits and risks matter most to you? (4) Do you have enough support and advice to make a choice? Demographic data related to age, race/ethnicity, family history of prostate or other cancer, and other pertinent health information will be collected.

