## 9.2 Analysis Plans

**Decisional Conflict to Consider Genetic Testing.** All study variables, such as demographics, PCA knowledge, and outcome responses, will be summarized in tables with descriptive statistics or graphically in data plots at each time they are assessed along with changes in responses over time. We will investigate imbalances in these data for potential confounding of primary and exploratory endpoint analyses and investigate disparities and intervention effect modification in various subgroups of subjects. The primary outcome is decisional conflict regarding genetic testing assessed by the 4-item SURE scale. To compute a summary decisional conflict score, the Likert-scaled responses will be averaged across the SURE item responses provided by a subject completing at least 2 of the 4 questions. The change in decisional conflict scores between baseline and endpoint at 2-months will be calculated and group means for these changes compared between subjects randomized to receive control materials vs. those randomized to receive the peer health education intervention (i.e., by intention to treat). The significance of the difference will be evaluated at the 0.05 level using a two-sided Student's t-test. The assumptions for this test will be carefully evaluated. If the changes are substantially skewed, they will be summarized with group medians and evaluated for significant differences by the nonparametric Wilcoxon's rank sum test. If concerns arise over potential confounding from imbalances in baseline covariates, we will conduct a sensitivity analysis by applying analysis of covariance (ANCOVA) to adjust the comparison for baseline imbalances, including baseline decisional conflict scores.

**Descriptive and Exploratory Analyses.** Exploratory analyses will include estimating the proportion of AA men meeting the NCCN guidelines for genetic testing and computing a 95% confidence interval using the Clopper-Pearson exact method. Summary statistics and qualitative analyses will be used to assess the genetic counseling experience of those subjects accepting the offer for genetic counseling. Additional analyses will include estimating the intervention effect on genetic testing/counseling intentions and uptake, respectively, changes in attitudes toward genetic testing, and understanding of personal genetic test results using discrete variable tests, such as McNemar's test.

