### 14.3 Participant Stipends or Payments

Aim 1: Participants will be compensated \$25 for attending a focus group.

Aims 2/3: Each man who participates in all study-related activities will receive \$50 over the course of the study. Men in the intervention group will receive \$25 for completing the baseline survey at the time of the health education session and \$25 for completing the endpoint survey over the telephone at two-months post-intervention. Men in the control group will receive \$25 after completing the baseline survey and an additional \$25 for completing the endpoint survey over the telephone at two-months post-intervention.

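### Nothing in the protocol keeps the 2-month telephone caller unaware of arm, although the call date follows an arm-specific event and the only primary outcome is four subjective answers

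*Combined protocol and SAP*

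**What the plan says.** Section 9.2 names one primary outcome: "The primary outcome is decisional conflict regarding genetic testing assessed by the 4-item SURE scale". It is analysed as the change from baseline to two months, compared between arms with a two-sided t-test at the 0.05 level. Section 6 (Baseline Survey) describes the instrument: "The four questions encompass the following with Yes/No responses: (1) Do you feel sure about the best choice for you", followed by three similar questions on knowing, weighing and being supported in the choice.

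Section 6 (Endpoint Survey) gives the collection rule: "A member of the study team will call each participant two months after either attending a peer education session (intervention arm) or being mailed" the print materials in the control arm. On content it says "The majority of items on the baseline survey, except for the demographic information, will be repeated on the endpoint survey". There is a fallback: "Participants who are not reached by telephone will be contacted by mail and by email". Telephone is nevertheless the expected mode, because Section 14.3 describes the second payment, in dollars and for both arms, as "25 for completing the endpoint survey over the telephone at two-months post-intervention".

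On staff, Section 6 (Study eligibility) says that men "will be screened for eligibility by the study research manager", and Section 6 (Baseline Survey) says "All participants will complete a brief baseline questionnaire over the telephone or in person with the study manager". The endpoint caller is identified only as a member of the study team. Section 13.2 has surveys completed on paper and entered into REDCap by a member of the study team. Section 3.3.1 says that the biostatistician supplies the randomisation scheme and does not say who may see the assignments.

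**The concern.** Participants in this trial cannot be blinded, since each man knows whether he attended a session or received a booklet. The person who collects the outcome can be masked, at least in part, and the protocol makes no attempt at this.

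Feeling sure, being clear and having enough support are judgements, and a hesitant reply over the telephone has to be turned into a Yes or a No. A caller who knows that a man attended the study's own session may probe differently, or settle a doubtful reply differently, from one speaking to a man who received a booklet. The hypothesis in Section 9.1 has a direction (less conflict after peer education), so any such tendency is more likely to favour the intervention than to cancel out. The planned safeguards in Sections 9.2 and 9.3 (intention to treat, covariate adjustment, multiple imputation, pattern mixture models) deal with other problems and would not remove it.

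**Working it through.** **1. Is masking provided anywhere?** The relevant sections, side by side:

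- Section 3.3.1 and Section 6 (Study Randomization and Informed Consent): assignment is described; masking of staff is not mentioned.
- Section 6 (Study eligibility, Baseline Survey): screening and baseline are given to the study (research) manager. Nothing says whether this person makes endpoint calls.
- Section 6 (recruitment and training of educators): peer educators are trained so that they can collect data during the intervention. Nothing says whether they may make endpoint calls.
- Section 6 (Endpoint Survey): the call date is counted from a session or a mailing. Nothing says what the caller sees.
- Sections 9.2 and 9.3: no masked assessor or masked analyst.
- Section 11: staff are to be trained on a manual of operating procedures. Its content on this point is not given.
- Section 13.2: data entry is by the study team, with no masking stated.

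Whoever builds the call list must use an event that identifies the arm, and no step stops that information from reaching the caller.

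**2. The plan's own figures.** Inputs from Section 9.3: difference 0.40, SD 0.76, two-sided alpha 0.05, power 90%.

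- n per arm = 2 × (1.960 + 1.282)² × 0.76² / 0.40² = 75.9, so 76 against the stated 75.
- Power at 75 per arm is 89.7% (normal approximation) or 89.3% (noncentral t).
- Attrition: 150 / 0.85 = 176.5, so 177 against 176; 176 × 0.85 = 149.6.

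The sample size reproduces to within rounding and is not affected by this point.

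**3. What a collection bias would do.** The documents give no size for it, so the values of b below are assumptions. Suppose there is no true effect, 75 men per arm, SD 0.76 applied to the change score, and a shift b favouring one arm.

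Standard error = 0.76 × √(2/75) = 0.124. Noncentrality = b / 0.124, with 148 degrees of freedom.

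| Assumed b | Noncentrality | Two-sided false-positive rate |
|---|---|---|
| 0.05 | 0.40 | 6.9% |
| 0.10 | 0.81 | 12.6% |
| 0.15 | 1.21 | 22.5% |
| 0.20 | 1.61 | 36.0% |

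**4. Why no single b can be defended.** Suppose one item changed to Yes in 10% to 20% of intervention men only (an assumption).

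- On a 0 to 4 count, the shift is 0.10 to 0.20, and 0.10/0.40 to 0.20/0.40 is 25% to 50% of the planned difference.
- Section 9.2 averages the items. With Yes/No scored 1/0, one item moves a man's score by 1/4 = 0.25, so the shift is 0.025 to 0.05, or 6.25% to 12.5% of the printed 0.40.
- The printed 0.40 comes with a reference mean of 3.77, which cannot lie on a 0 to 1 average, so this second ratio mixes scales. The documents describe the items as Yes/No in Section 6 and as Likert-scaled in Section 9.2, and do not settle the matter.
- If 3.77 is on a 0 to 4 count with higher scores meaning less conflict, the room left is 4 − 3.77 = 0.23. A shift of 0.10 to 0.20 would then need 43% to 87% of the remaining No answers to change. Baseline scores in this trial may be lower than in that reference group.

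**The case against.** The strongest reply is that the protocol is silent rather than wrong. The Endpoint Survey text fixes when the call is made, not what the caller is told, and a scheduler could pass on a due date alone. Section 11 promises a manual covering all study tasks, and the Appendices say that the surveys will be added later, so scripting and item order may be settled there. This stands as far as it goes: a reader might infer that the caller knows the arm, but no passage says so. It does not remove the point, because the protocol neither requires masking nor refers to it.

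Two other inferences are tempting and are not supported. One is that the same few people screen, schedule, send booklets and make the endpoint calls. The documents name the manager for screening and baseline only, do not say who schedules sessions or sends booklets, and include clinic personnel in the team (Section 6.1.1). The other is that every SURE answer is read out and recorded by a caller. Follow-up by mail and email may produce some self-completed surveys.

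It can also be said that masking would achieve only part of what is wanted. Sessions of about 6 to 8 men, once or twice a month, make due dates cluster, so an exact date could reveal the arm. Men may mention the session or booklet, and their own reporting stays unblinded. All of this is correct. It shapes the remedy but does not argue against having one.

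**Conclusion.** The point holds in this form: the protocol leaves the collector of a subjective primary outcome unmasked by default, under a scheduling rule that makes awareness of arm likely. The resulting bias could favour the intervention and would not shrink with sample size.

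Its size cannot be estimated. The false-positive rates of 6.9% to 36.0% show only how sensitive the test is to assumed shifts of 0.05 to 0.20 units; they do not forecast what will happen. A reader might go further and conclude that a quarter to a half of the planned 0.40 difference could be artefact. That rests on assumed percentages of men, a shift confined to one arm and a 0 to 4 count that Section 9.2 does not use, so it should not be cited as a finding.

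The change is worth making as an inexpensive improvement to the primary outcome. The sample size does not need to change.

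**What to change.** Amend the Endpoint Survey text in Section 6 as follows.

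- Where current staffing allows, endpoint calls are made by an existing team member who does not randomise, schedule or attend sessions, or send booklets.
- The caller works from a list showing only participant ID and a call window. The exact trigger date is left off because session dates cluster.
- A verbatim script asks the four SURE items before any question about the session or booklet.
- The caller records the mode of completion (telephone, mail or email) and whether the arm was revealed before SURE was finished.
- If no masked caller is available, keep the verbatim script with SURE first, and report caller awareness as a limitation.

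The cost is some reallocation of tasks, a restricted call list and a fixed question order, with slightly less flexibility in scheduling. No participants, visits or procedures are added. The documents give no staffing list, so whether a suitable caller exists is for the study team to confirm. Bias from participants' own reporting will remain and should be acknowledged.

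### The intervention-arm endpoint call is dated only from attending a session, so men who never attend have no call date, and the payment text conflicts with the procedures on when and how that arm's baseline is taken

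*Combined protocol and SAP*

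**What the plan says.** **Endpoint.** The Endpoint Survey paragraph of section 6 states that "All men, regardless of study arm, will complete an endpoint survey". It then times the telephone call "two months after either attending a peer education session (intervention arm) or being mailed the educational print materials (control arm"). Mail and email are the fallback for men whom the telephone does not reach.

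**Attendance.** The randomization paragraph of section 6 says "Men randomized to the intervention arm will be scheduled to attend a health education session hosted at CityLife Clinic or virtually". The Intervention Arm paragraph says these men are invited. Attendance is therefore an event after randomization that may not happen.

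**Baseline.** The Baseline Survey paragraph says "All participants will complete a brief baseline questionnaire over the telephone or in person with the study manager". The Control Arm paragraph gives an order: "After providing informed consent and completing the baseline survey over the telephone or in-person, eighty-eight men will be randomized to this arm". For the intervention arm, the Participant Compensation paragraph pays $25 "for completing the baseline survey via the mail", and section 14.3 pays $25 "for completing the baseline survey at the time of the health education session".

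**Analysis.** Section 9.2 compares the mean change in SURE score from baseline to 2 months between the arms as randomized. Section 9.3 says that multiple imputation will be considered, and that sensitivity analyses will be done if more than 10% of any outcome is missing.

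**The concern.** The primary outcome is a change score, so each randomized man needs both a baseline and a 2-month SURE. In the control arm, both are tied to things the study team does. In the intervention arm, the endpoint date depends on something the participant does, and one payment paragraph ties the baseline to the same event.

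If staff followed section 14.3 as written, the intervention baseline would be taken after allocation and only from men who came to a session. If they also followed the endpoint trigger literally, a non-attender would have neither survey. The only other SURE measurement, the survey straight after the session discussion, would miss him too. The analysis would then compare attenders in one arm with all men in the other, and imputation would have no SURE score from the absent men to work from.

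**Working it through.** **1. The plan's own figures.** Inputs from section 9.3: SD 0.76, difference 0.40, two-sided 5% level, 90% power, 75 analysed and 88 randomized per arm, about 15% attrition.
- n per arm = 2 × (1.960 + 1.282)² × (0.76/0.40)² = 75.9, so 76 by the normal approximation. The exact t calculation gives 77. Power at 75 per arm is 89.7% (normal) or 89.3% (t).
- 176 × 0.85 = 149.6, against the stated 150.

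The stated figures reproduce to within rounding, and this point does not dispute them.

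**2. Is there a call date for a non-attender anywhere?**
- Endpoint Survey paragraph: two months after attending. He has no such date.
- Both payment paragraphs: two months after the intervention. He has no such date.
- Section 9.2: an endpoint at 2 months, with no starting event.
- Section 3.3 gives about 2 months in the study, and the Study Summary gives 1-3 months. Neither names a starting event.
- Mail and email fallback: covers men who cannot be reached, not men with no date.

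No section supplies one. Because men are invited, a man who never books may not have a scheduled session date either.

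**3. Baseline, side by side.**
- Baseline Survey paragraph: all men, by telephone or in person, with the study manager.
- Participant Compensation paragraph: intervention arm, by mail.
- Section 14.3: intervention arm, at the session.
- Section 13.2: paper-and-pencil collection, which fits any of these.
- Control Arm paragraph: consent, baseline, then randomization. A man's arm is unknown until he is randomized, and each man is randomized once, so this order must hold for every man.

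Section 14.3 therefore conflicts with the procedures on both place and order, and the Participant Compensation paragraph conflicts on mode.

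**4. Illustration under assumed rates.** Let q be the share of the intervention arm that never attends. The documents give no value; 5-20% is assumed.
- Planned allowance: 88 − 75 = 13 men per arm; 13/88 = 14.8%.
- If q is additional to 15% attrition and no non-attender is called, the missing share is 1 − (1 − q) × 0.85:
  - q = 5%: 19.25% (16.9 of 88)
  - q = 10%: 23.5% (20.7 of 88)
  - q = 20%: 32.0% (28.2 of 88)
  - controls: 0.15 × 88 = 13.2 men
- Omitting non-attenders shifts the intervention mean by q × (attender change minus non-attender change). If that gap were the full 0.40 (assumed), the shift is 0.02, 0.04 and 0.08 at q = 5%, 10% and 20%, which is 5%, 10% and 20% of the target. It is zero if the two groups change alike.
- Power is not the main issue. With the effect held at 0.40, analysing 68 v 75 men (q = 10%) gives 87.7%, and 60 v 75 (q = 20%) gives 85.5%. What is lost is comparability with the randomized control arm.

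**The case against.** The protocol's intent is clear. It wants an endpoint survey from all men, says each participant will be called, and analyses by intention to treat. A reader might infer that non-attenders are excluded from follow-up. The documents do not support that: the rule is unstated, and nothing excludes these men. The manual of operating procedures promised in section 11 may supply the date.

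A reader might also infer that the order of baseline and allocation is left open in the intervention arm, or is deliberately different there. That does not hold either, because the control-arm sequence must apply to every man before his arm is known. The conflicting wording is confined to payment text, which may describe only how or when the $25 is paid.

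The 15% attrition allowance may already include men who never attend, in which case the total loss is as planned. The control trigger refers to mailing although a booklet may also be "provided to the participant in person"; this is trivial, since the handover date is known.

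Most of this stands and limits the weight of the point. Three things remain. The timing of the primary outcome belongs in the protocol and not only in a manual. The payment sentences describe the endpoint survey by how it is done (telephone), so reading the baseline phrase in the same way is natural. A manual also cannot resolve conflicting protocol text without departing from one version of it.

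**Conclusion.** Two textual defects stand: there is no call date for intervention men who never attend, and the payment wording contradicts the procedures on that arm's baseline. Harm follows only if staff act on the literal trigger or on section 14.3. Acting on both would confine the primary change score to attenders in one arm.

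The size and direction of any bias cannot be stated. The 19-32% missing and the 0.02-0.08 shift are not forecasts. The first rests on assumed non-attendance of 5-20%, no calls to those men, and a further 15% attrition among the rest; the second on the same non-attendance range and an attender/non-attender gap equal to the whole target difference. If the 15% already covers non-attendance, the total is as planned and only the reasons for loss differ between the arms.

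The expected 15% attrition already exceeds the 10% level in section 9.3, so the sensitivity analyses would be run. They do not replace data that a telephone call could collect. Severity: minor to moderate. Confidence is high on the text and low on any practical effect.

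**What to change.** (a) State once, for both arms, that the baseline SURE is completed with the study manager, by telephone or in person, before the allocation is revealed. Align the Participant Compensation paragraph and section 14.3 with that.

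(b) In the Endpoint Survey paragraph, keep two months after the session for attenders. For men who never attend or never book, set a call date in advance that does not move with later rescheduling, for example two months after the first session date offered, or a set interval from randomization. For controls, write mailing or handover. Call all randomized men, keep them in the intention-to-treat analysis, and report attendance and missing outcomes by arm.

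If surveys are already under way or finished, document the rule that was used and report the same two items.

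**Cost.** Protocol wording and some calls: 0.05 × 88 = 4.4 to 0.20 × 88 = 17.6 men at the assumed rates, or $110 to $440 at the $25 endpoint payment already offered. The baseline-to-endpoint interval may differ somewhat between attenders and non-attenders. Including men who had no session dilutes the effect, but the planned intention-to-treat analysis already implies that. The sample size, test and intervention do not change.
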